### 6. TREATMENTS

This is a non-drug study and therefore no study treatment (IMP or non-IMP) will be administered.

# 6.1 MEASURES TO MINIMIZE BIAS: RANDOMIZATION AND BLINDING

There will be no randomization and no blinding

#### 6.2 CONCOMITANT THERAPY

For participants with ASD any stable prescribed medication at screening should remain stable throughout the study. However, dose changes due to adjustments for change in body weight/ age and or triggered by therapeutic monitoring will be allowed. Other changes in prescribed medication need to be approved by the Sponsor (Medical Monitor or designee).

For TD healthy participants as a general rule, no concomitant therapies will be permitted, with the exception of medications to treat adverse events. However, approval for concomitant therapies can be obtained on case by case basis after discussion between the Investigator and the Sponsor (Medical Monitor or designee). The case needs to be clearly documented.

# 6.2.1 Permitted Therapy for Participants with ASD

Any medication or vaccine (including over-the-counter [OTC] or prescription medicines, approved dietary and herbal supplements, nutritional supplements) used by a participant

from 12 weeks prior to screening until the follow-up visit must be recorded along with reason for use, dates of administration (including start and end dates) and dosage information (including dose and frequency). Details of psychosocial/non-pharmacological interventions used over the past year are to be documented in detail see section 6.2.2.

The Sponsor (Medical Monitor or designee) should be contacted if there are any questions regarding concomitant or prior therapy. All concomitant medications should be reported to the Investigator and recorded on the Concomitant Medications electronic Case Report Form (eCRF). All therapy and/or medication administered to manage adverse events should be recorded on eCRF.

# 6.2.2 Non-Pharmacological Interventions for Participants with ASD

Non-pharmacological interventions (e.g., subject psychotherapy, cognitive behavioral therapy, applied behavioral analysis [ABA], speech therapy, occupational therapy, rehabilitative therapy, and social skills training) must be stable for 6 weeks prior to screening and must remain stable throughout the ongoing study in terms of type of intervention and intensity. Minor changes in ongoing treatment (e.g., missed therapy sessions due to holiday/vacation; planned break in therapy due to school holidays; changes in college/school programs) are not considered significant and need not to be discussed with the Sponsor (Medical Monitor or designee).

A complete history of non-pharmacological interventions for the treatment of ASD including all previously completed therapies will be reported on eCRF and will include start and end date, name of therapy and number of hours per week.

### 7. PARTICIPANT DISCONTINUATION/WITHDRAWAL

An excessive rate of withdrawals can render the study non-interpretable. Therefore, unnecessary withdrawal of participants should be avoided and efforts should be taken to motivate participants to comply with all the study specific procedures as outlined in this protocol.

Details on study and site closures are provided in Appendix 1.

# 7.1 PARTICIPANT DISCONTINUATION/WITHDRAWAL FROM THE STUDY

Participants have the right to voluntarily withdraw from the study at any time for any reason.

In addition, the Investigator has the right to withdraw a participant from the study for medical conditions that the Investigator or Sponsor determines, may jeopardize the participant's safety if he/she continues in the study.

If possible, information on reason for withdrawal from the study should be obtained. The primary reason for withdrawal from the study should be documented on the appropriate eCRF. Participants will not be followed for any reason after consent has been withdrawn.

Only participants who withdraw from the study before completion of the week 2 visit will be replaced (in the same cohort).

See SoA (Section 1.2) for data to be collected at the time of early withdrawal visit.

#### 7.2 LOST TO FOLLOW-UP

A participant will be considered lost to follow-up if the participant repeatedly fails to return for scheduled visits and is unable to be contacted by the study site.

The following actions must be taken if a participant fails to return to the clinic for a required study visit:

- The site must attempt to contact the participant and reschedule the missed visit as soon as possible, counsel the participant on the importance of maintaining the assigned visit schedule and ascertain whether or not the participant wishes to and/or should continue in the study.
- Before a participant is deemed lost to follow-up, the Investigator or designee must make every effort to regain contact with the participant. These contact attempts should be documented in the participant's medical record.
- Should the participant continue to be unreachable, he/she will be considered to have withdrawn from the study.

Discontinuation of sites or of study as a whole are handled as part of Appendix 1.

# 8. STUDY ASSESSMENTS AND PROCEDURES

Study procedures and their time-points are summarized in the Schedules of Activities (SoA; Section 1.2). Protocol waivers or exemptions are not allowed.

#### 8.1 EFFICACY ASSESSMENTS

### 8.1.1 Clinical Outcome Assessments

Caregivers, clinicians and participants will use an electronic device to capture clinical outcome assessments (COA) specified below (see Appendix 1; 2.1.2.1.). The sequence of assessments specific for each age cohort is pre-defined on the electronic device for each participant and should be followed throughout the study. During the administration interview of the VinelandTM-II, MERS-R, and the CYBOCS-ASD audio recordings will be captured. These audio recordings will be reviewed by central clinicians to verify if these scales were administrated

according to the rating standards. If necessary, raters will be contacted for remediation and additional training. It is not planned to extract any information about participant and caregiver from these audio recordings.

Any entries on COA should be reviewed for completeness by site staff during the visit and caregiver and participants should be requested to complete any blank items. If a scale cannot be completed during the visit or for a scale the total score (e.g., the composite scores for VinelandTM-II) cannot be calculated with the available data, it should be tried to repeat the scale during an unscheduled visit within up to approximately 2 weeks.

Table 4 Overview Clinical Scales/Clinical Outcome Assessments

Scale group	Specific scale	Completed by	Children	Adolescents	Adults	Time [min]
	. Stanford-Binet	clinician	mandatory	mandatory	mandatory	15-20
ADOS-2		clinician	mandatory	mandatory	mandatory	40-60
CGI-I+CGI-S		clinician	mandatory	mandatory	mandatory	5+5
CY-BOCS-ASD		clinician	mandatory	mandatory	mandatory	~ 20
MERS-R		clinician	mandatory	mandatory	mandatory	15-20
RBS-R		caregiver	mandatory	mandatory	mandatory	~ 15
RBQ-2 	RBQ-2 for Children	caregiver	mandatory	mandatory	if deemed appropriate  by Investigator	20-30
	RBQ-2A for adults	participant- reported		if deemed appropriate  by Investigator based on mental age.	mandatory	20-30
Routine Inventory 	CRI-R for Children	caregiver	mandatory	mandatory	if deemed appropriate  by Investigator	~ 17
	ARI for adults	participant- reported		if deemed appropriate  by Investigator based on mental age	mandatory	~ 17
BRIEF	BRIEF for children	caregiver	mandatory	mandatory		10-15
	BRIEF-A for adults	caregiver	-		mandatory	10-15
Vineland™-II (survey)		clinician	mandatory	mandatory	mandatory	45-60
	Family Impact Scale	caregiver	mandatory	mandatory	mandatory	~ 5
PedsQL	Generic Core & Cognitive Functioning Scales	participant- reported	mandatory	mandatory	mandatory	~10

Table 4 Overview Clinical Scales/Clinical Outcome Assessments (cont.)

Scale group	Specific scale	Completed by	Children	Adolescents	Adults	Time [min]
SSP	Short Sensory profile	caregiver	mandatory	mandatory	a.	5-15
Sleep 	CSHQ	caregiver	mandatory	mandatory	if deemed appropriate  by Investigator	5-10
	PSQI	participant- reported		if deemed appropriate by Investigator 	mandatory	~ 5
RMET 	RMET-C for Children	participant- reported	if deemed appropriate  by Investigator	if deemed appropriate  by Investigator	if deemed appropriate  by Investigator	~ 20
	RMET-R for adults	participant- reported		if deemed appropriate  by Investigator	if deemed appropriate  by Investigator	~ 20
Anxiety 	HAM-A	clinician	 		mandatory	10-15
	PRAS-ASD	caregiver	mandatory	mandatory		~ 10
	BAI	participant- reported		if deemed appropriate  by Investigator	mandatory	5

 For scales where a pediatric and an adult scale or scale version exists, both versions should be administered in adolescents and adults, if deemed appropriate by Investigator. For further details, see protocol Section 8.1.1.3. In any case, at least one scale / scale version will be mandatory.

# 8.1.1.1 Requirements for Caregivers

All disease specific clinical outcome assessments (see Table 4 and Table 1) will take place on-site at the clinic. The same caregiver will provide feedback on all informant-based assessments throughout the study and the same caregiver must attend all on-site visits. If a caregiver visit cannot be completed as arranged – e.g., the caregiver is delayed in transit – visits should be rescheduled as soon as possible after the original appointment. Caregiver-completed assessments cannot be conducted over the telephone. Caregiver initials will be reported on eCRF at all assessments.

The reliable caregiver or parent must live with the participant or have substantial and sufficient periods of contact with the participant and is willing and able to attend the onsite visits when required. The reliable caregiver or parent must oversee the participant's adherence with protocol-specified procedures, and report on the participant's status via completion of study assessments.

If the caregiver is not living with the participant, the Investigator has to be satisfied that the participant can contact the caregiver readily during the times when the caregiver is not with the participant. If in doubt about whether a participant's care arrangements are suitable for inclusion, the Investigator should discuss this with Sponsor (Translational Medicine Leader or designee). A non-cohabitating caregiver must spend sufficient time with the participant so that, in the opinion of the Investigator, the caregiver can reliably

 For the RMET, either the pediatric or adult version should be administered. If none of the two RMET versions is deemed appropriate for the participant the RMET can be skipped.

assess the participant's mental status, activities and behavior, and report on the participant's adherence and health. This would normally be possible when the caregiver spends a few hours each day with the participant.

The caregiver arrangements for participants living in a residential home need to be assessed carefully on a case by case basis:

- A staff member of the residential home can be the caregiver if this person spends
   sufficient time with the participant. In the opinion of the Investigator, the caregiver must
   be able to reliably assess the participant's mental status, activities, and behavior, and
   report on the participant's adherence and health. This would normally be possible when
   the caregiver spends a few hours each day with the participant.
- A family member living at the participant's home can be the caregiver if the participant returns home every night. When the participant returns home only over the weekend, a family member can only be the caregiver if they have intensive interaction with the participant during the week e.g., via phone calls, calls via Skype, SMS messages, etc. The quality of these interactions between caregiver and participant needs to be assessed for each participant to determine whether they are sufficient.
- A family member cannot be the caregiver when the participant lives full time in the residential home, unless the family member spends a few hours each day with the participant in the residential home.

If in doubt about whether a participant's care arrangements are suitable for inclusion, the Investigator should discuss this with the Sponsor (Translational Medicine Leader or designee).

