# 8.1.1.14 PedsQL Family Impact Scale

The Pediatric Quality of Life Inventory (PedsQL™) Family Impact Module version 2 (Varni et al 2004) is a 36-item questionnaire which is completed by the caregiver and was developed to measure parent and family functioning. It encompasses six scales covering 1) Physical Functioning (6 items), 2) Emotional Functioning (5 items), 3) Social Functioning (4 items), 4) Cognitive Functioning (5 items), 5) Communication (3 items), 6) Worry (5 items), and two scales measuring parent reported family functioning; 7) Daily Activities (3 items) and 8) Family Relationships (5 items). For each item a 5-point response scale is utilized (0=never a problem; 4=always a problem). Items are then reverse-scored and linearly transformed to a 0−100 scale (0= 100, 1= 75, 2= 50, 3= 25, 4= 0), so that higher scores indicate better functioning (less negative impact).

Scale Scores are computed as the sum of the items divided by the number of items answered (this accounts for missing data). If more than 50% of the items in the scale are missing, the Scale Score is not computed. A total score, a Parent HRQOL Summary Score, and a Family Summary Score can also be computed by averaging across the relevant domains (total score by averaging across all items, Parent HRQOL Summary Score by averaging the 20 items in Physical, Emotional, Social, and Cognitive Functioning, and the Family Summary Score by averaging eight items in Daily Activities and Family Relationships). The acute form with a recall period of 7 days will be employed in this trial.

It will take the caregiver approximately 5 minutes to complete the PedsQL family impact scale.

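### Residential-home staff can be the sole caregiver informant, yet the mandatory PedsQL Family Impact Scale has no not-applicable rule and no analysis rule for caregivers outside the family

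*Combined protocol and SAP*

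**What the plan says.** Four parts of the protocol bear on this.

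- **Who may be the caregiver (Section 8.1.1.1).** "A staff member of the residential home can be the caregiver", provided that person spends enough time with the participant. For full-time residents the family route is largely closed: "A family member cannot be the caregiver when the participant lives full time in the residential home", unless that relative spends a few hours there each day.
- **One informant for everything (Section 8.1.1.1).** "The same caregiver will provide feedback on all informant-based assessments throughout the study".
- **Status of the scale (Table 4 in Section 8.1.1, and Table 1).** The Table 4 row reads "Family Impact Scale caregiver mandatory mandatory mandatory", the last three entries being children, adolescents and adults. It has no footnote and no investigator-discretion clause. Table 1 schedules the scale at Baseline, Week 2, Week 12 and early withdrawal.
- **What the scale measures (Section 8.1.1.14).** It is "completed by the caregiver and was developed to measure parent and family functioning". Six of its eight subscales are Physical, Emotional, Social and Cognitive Functioning, Communication and Worry. The others are "two scales measuring parent reported family functioning": Daily Activities and Family Relationships.

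On the data side, Section 8.2.1 records the caregiver's relationship to the participant, and Section 9.2.1 lists caregiver status among the baseline characteristics. Section 9.2.4 covers the correlation structure between scales and leaves further detail to a technical document that is not among the documents reviewed.

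**The concern.** Taken together, these rules require a paid carer to fill in a questionnaire about a parent's own functioning and a family's life. The form can be completed and scored, so nothing in the data would look wrong. The score would nevertheless describe the staff member, the staff member's own household, or a guess about the participant's family.

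The situation is foreseeable. The Version 2 amendment rationale says the residential-home guidance was needed because some participants, particularly those with low IQ, may live in such homes. Three of the six ASD cohorts, about 45 of 90 participants, are recruited at ABIQ 50 to below 70. If staff informants cluster there, informant type would be partly mixed up with IQ.

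At stake are summaries of this one scale and, if it is included, two secondary objectives: correlations between scales and the factor structure within each scale.

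**Working it through.** **Step 1: is there a way out for a staff caregiver?**

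| Possible exit | What the protocol provides |
|---|---|
| Another respondent for this scale | No; the same caregiver answers all informant-based scales (8.1.1.1) |
| Skip rule | Covers participant-reported scales (8.1.1.2), the RMET (Table 4, footnote 2) and unsuitable digital assessments (8.4.1), not this scale |
| Leave items blank | "caregiver and participants should be requested to complete any blank items" (8.1.1); if the total score cannot be calculated, an attempt is to be made to repeat the scale at an unscheduled visit |
| Waiver | Section 8 rules out waivers and exemptions |
| Case-by-case review of residential arrangements | Concerns how well the caregiver knows the participant, not whether the caregiver belongs to the family (8.1.1.1) |

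None applies.

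**Step 2: how much of the scale is affected?** Item counts are from Section 8.1.1.14.

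- All items: 6 + 5 + 4 + 5 + 3 + 5 + 3 + 5 = 36, matching the stated total.
- Parent HRQOL Summary: 6 + 5 + 4 + 5 = 20, as stated.
- Family Summary: 3 + 5 = 8, as stated.
- Items entering one of these two summaries: (20 + 8)/36 = 28/36 = 78%. The other 8 (Communication 3, Worry 5) enter the total score.

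**Step 3: how many participants?** The documents do not say. As an assumption, 1, 5 or 10 staff informants among 90 would be 1.1%, 5.6% or 11.1%.

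**Step 4: illustration of the effect on a correlation, if scores were pooled.** Every input here is an assumption. S is repetitive-behavior severity and F the Family Impact score (higher is better), both standardised among participants with family caregivers.

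- ρ = -0.40 among families.
- Staff scores have variance 0.5 and no correlation with S.
- Residential participants are s = 0.5 SD more severe.
- p is the share of staff informants; g is the staff-minus-family mean gap in F, in SD.

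Formulas:

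- Cov = (1-p)ρ + p(1-p)gs
- Var(F) = (1-p) + 0.5p + p(1-p)g²
- Var(S) = 1 + p(1-p)s²
- r = Cov / √[Var(F) × Var(S)]

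For p = 0.10, p(1-p) = 0.09 and Var(S) = 1 + 0.09 × 0.25 = 1.0225.

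- g = 0: Cov = -0.36; Var(F) = 0.95; r = -0.36/√0.9714 = -0.37.
- g = 0.5: Cov = -0.36 + 0.0225 = -0.3375; Var(F) = 0.9725; r = -0.3375/√0.9944 = -0.34.
- g = 1.67: Cov = -0.36 + 0.0752 = -0.2848; Var(F) = 1.2010; r = -0.2848/√1.2280 = -0.26.

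The same formulas over a range of shares give:

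| Staff share p | g = 0 | g = 0.5 | g = 1.67 |
|---|---|---|---|
| 5% | -0.38 | -0.37 | -0.32 |
| 10% | -0.37 | -0.34 | -0.26 |
| 20% | -0.33 | -0.28 | -0.16 |

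A single staff informant (p = 1/90) with g = 1.67 gives -0.38. Reversing the sign of the gap (g = -0.5, p = 0.10) gives Cov = -0.36 - 0.0225 = -0.3825 and r = -0.3825/√0.9944 = -0.38. The size therefore depends on the sign as well as the magnitude of a gap that the documents do not give.

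**The case against.** The strongest reply is that this is a small matter in an exploratory, unpowered study. The scale is not a repetitive-behavior scale, the number of staff caregivers may be zero, and Section 9.2.4 treats p-values descriptively only. At n = 90 an approximate 95% interval for r = -0.40 runs from -0.56 to -0.21 (Fisher: -0.424 ± 1.96/√87), so every illustrative value at a 5% or 10% share lies within sampling error. The 20% case would need 18 staff caregivers, which is 40% of the planned 45 participants with ABIQ below 70, and nothing supports that. All of this stands, and it limits severity.

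A reader might infer more than the documents support:

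- **That staff and family scores will be pooled.** No section says so. Pooling is only what happens if nothing separates them; the technical document might do so, and the recorded relationship makes it possible.
- **That this scale certainly enters the planned analyses.** The descriptive summaries in Section 9.2.3 are specified for the repetitive-behavior scales. Section 9.2.4 does not list which scales are correlated, and no analysis of severity against family burden is named.
- **That Version 2 made staff newly eligible.** The amendment rationale describes clarified guidance, and inclusion criterion 3 admits a parent or another reliable caregiver.
- **That the bias runs in a known direction.** Nothing says how staff would answer, and residential living is linked to low IQ, not to more severe repetitive behavior.

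What the reply does not remove is the conflict itself. A technical document can repair an analysis, but it cannot stop a staff member from being required to answer about family life.

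**Conclusion.** The conflict between the caregiver rules and the mandatory Family Impact Scale is in the current text and has no exit. Scores from staff caregivers would not measure the intended construct, and no stated rule omits, flags or separately analyses scores from non-family caregivers. This rests on the wording of Sections 8.1.1, 8.1.1.1 and 8.1.1.14 and needs no numerical assumption.

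Exposure is confined to summaries of this scale and, if it is included, the secondary between-scale correlation and within-scale factor analyses. The frequency, direction and size of any distortion cannot be derived from the documents; the correlations shown are illustrations. Severity is minor: a cheap improvement.

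**What to change.** Add a footnote to the "Family Impact Scale" row of Table 4 and a matching sentence in Section 8.1.1.14: the scale is completed only when the designated caregiver is a parent or family member; otherwise it is recorded as not applicable and is not administered.

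For data already collected, state in the technical document that Family Impact analyses are restricted to family caregivers, identified from the relationship recorded under Section 8.2.1, and report how many participants this leaves out.

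The cost is one footnote, one protocol sentence and one analysis-set sentence, with no new data collection. The downside is that a few participants will have no Family Impact score, so results for this scale will describe only participants with a family caregiver. The affected caregivers are spared about 5 minutes at each visit where the scale is scheduled.

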# 8.1.1.2 Administration of Participant-reported Scales to Illiterate Participants

For participants who are illiterate or have reading deficits the following procedure for the mandatory participant-reported scales should be used:

- The scale administrator will read out the questions and answers and show the answers on the Rater station.
- The participant will choose one of the possible answers on the Rater station.
- If the participant is still unable to complete the scale even with the described assistance, the scale will be skipped. For adult participants only: where a similar caregiver-reported scale exists, that caregiver-reported scale will be completed instead of the skipped scale if it is deemed appropriate by Investigator (i.e., RBQ-2 if RBQ-2A is skipped, CRI-R if ARI is skipped, CSHQ if PSQI is skipped).

# 8.1.1.3 Administration of both the Caregiver and Participant-reported Scale Version "if deemed appropriate by Investigator"

For adolescents and adults both versions of the Routine Inventories and the Repetitive Behavior Questionnaires scale should be administered in individual participants at the same visit if the Investigator deems the non-mandatory version of the scale appropriate (see Table 4 and Sections 8.1.1.10 and 8.1.1.11). This includes the participant-reported adult versions (RBQ-2A and ARI) and the caregiver-completed pediatric versions (RBQ-2 and CRI-R).

- For adolescent participants the caregiver-completed RBQ-2 and CRI-R are mandatory scales. The participant-reported versions RBQ-2A and ARI will be completed as well, if deemed appropriate, and if the Investigator deems the participant able to complete these scales based on mental age.
- For adult participants the self-reported versions RBQ-2A and ARI are mandatory scales.
   The caregiver-reported RBQ-2 and CRI-R will be completed as well, if deemed appropriate by Investigator.

Similarly, and "if deemed appropriate by Investigator," the caregiver will complete the CSHQ for adult participants- Adolescent participants will complete the participant-reported PSQI and BAI (see Table 4).

If an adult participant is unable to complete a self-reported adult scale (e.g., because of mental age or other reasons) the corresponding caregiver-reported scale version will be used if it is deemed appropriate by Investigator and if such a scale version exists (i.e., RBQ-2 is to be completed if RBQ-2A is skipped, CRI-R if ARI is skipped, CSHQ if PSQI is skipped).

